Best Practice Alert (BPA) for Low Dose Aspirin Recommendation in High-Risk Pregnancies: a
Randomized Controlled Trial

Study Protocol with Statistical Analysis Plan

NCT05802940

06/05/2023

Study Protocol

Scientific Background

Preeclampsia is a significant cause of maternal morbidity and mortality, affecting up to 8% of pregnancies worldwide. Low dose aspirin (LDA) has been found to reduce the incidence of preeclampsia in high-risk pregnant patients.

Objectives

Upon internal review of electronic health record (EHR) data at our institution, we found that the recommendation for LDA use in high-risk pregnant patients was 60%. We hypothesize that the implementation of the EHR Best Practice Alert (BPA) will increase the healthcare provider's recommendation for LDA compared to the current standard care.

Design

We propose an RCT to assess the effect of an EHR clinical decision support (CDS) tool, specifically a BPA, on healthcare provider recommendations for low dose aspirin in high-risk pregnant patients.

Methods

Pregnant patients who receive and initiate prenatal care within Geisinger prior to 28 weeks gestation will be included if they are considered at high-risk of preeclampsia based on the modified United States Preventive Services Task Force (USPSTF) and American College of Obstetrics and Gynecology (ACOG) criteria listed above. Eligible patients will be randomized in a 1:1 fashion to a control or experimental group. In the control group, the women's health care provider will not receive a BPA; the pregnancy management will be based on the healthcare provider's current practice and knowledge. In the experimental group, the women's health care provider will receive a BPA in the EHR noting that the patient is at high-risk for preeclampsia and that the provider should recommend LDA. If LDA is not recommended, there will be a required acknowledgment reason from the provider noting a rationale for not initiating LDA. We defined women's health care provider as one of the following obstetric care providers who are able to prescribe medications: physicians (including resident physicians), physician assistants, certified registered nurse practitioners, and/or certified nurse midwives. Maternal-Fetal Medicine visits are excluded.

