In the experimental group, when the BPA fires, the provider can either accept the BPA recommendations (to prescribe LDA and to add this medication to the medication list) OR the provider can reject the BPA. If the BPA is rejected, the provider must choose a reason for rejection, i.e., patient declined, patient allergic to aspirin, patient taking aspirin, patient does not meet ACOG criteria for LDA, and Other (with comment). These specific rejection reasons will be reviewed by study team members on an on-going basis, so that the algorithm can be updated if needed to ensure it is only applying to those patients for whom LDA should be recommended.

Power Analysis

A total of 640 patients will be required to yield an adequate power to show a statistically significant difference in LDA recommendation rate. However, we plan to enroll an additional 10% to account for possible early miscarriages and early terminations.

Project Status

Patients will be randomized to study arms as they showed up to their appointments with an anticipated start date of June 19, 2023. Data collection is ongoing until the primary outcome date of June 19, 2025 (after the conclusion of pregnancy for all enrolled patients).

Statistical Analysis Plan

Planned Analyses

Primary Outcome: *A sensitivity analysis of the healthcare provider recommendation for low dose aspirin use in patients, specifically those who deliver after 28 weeks*
[Time Frame: Assessed between initial prenatal visit and delivery after 28 weeks]

Outcome Description: Patient chart indicates that the provider recommended aspirin (yes/no) between the day of the initial prenatal visit and delivery (≥ 28 weeks). The outcome is captured either by aspirin being added to the patient's medication record or via a prespecified algorithm searching notes for text strings such as "LDA," "ASA," "baby aspirin," etc. As per ACOG, low dose aspirin therapy should be initiated between 12 and 28 weeks, therefore we limited this outcome to patients who deliver after 28 weeks to ensure the provider had the entire window that ACOG allows to make the recommendation for low dose aspirin initiation.

Question: Does a BPA, which identifies patients as HRPP and recommends and facilitates LDA prescribing, that fires during prenatal visits increase the likelihood of LDA recommendation/prescribing in comparison with no BPA firing?

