Secondary Outcome: *The healthcare provider recommendation for low dose aspirin use in all randomized patients* [Time Frame: Assessed between initial prenatal visit and conclusion of pregnancy]

Outcome Description: Patient chart indicates that the provider recommended aspirin (yes/no) between the day of the initial prenatal visit and delivery (or conclusion of pregnancy). The outcome is captured either by aspirin being added to the patient's medication record or via a prespecified algorithm searching notes for text strings such as "LDA," "ASA," "baby aspirin," etc. This outcome will take into consideration all patients randomized, including those whose pregnancies resulted in termination, miscarriage or preterm delivery prior to 28 weeks. This intention-to-treat outcome will help assess the effect of the BPA in all patients.

Other pre-specified outcome measures

Outcome 1: *Patient taking low dose aspirin* [Time Frame: Assessed at time of delivery (≥ 28 weeks)]

Outcome Description: Patient chart indicates that the patient took aspirin (yes/no) during the pregnancy and up until delivery (≥ 28 weeks). The outcome is captured by aspirin being on the qualifying patient's medication record.

Outcome 2: *Rate of preeclampsia* [Time Frame: Assessed at time of delivery]

Outcome Description: Patient chart indicates that the patient experienced preeclampsia (yes/no) during the pregnancy, up until delivery. The outcome will be assessed at two time points, ≥ 28 weeks (so that patients were allowed the full window for low dose aspirin initiation) and ≥ 20 weeks (excluding miscarriages and earlier terminations of pregnancy). The outcome is captured by a diagnosis of preeclampsia on the qualifying patient's chart noted either by chart review or an algorithm that was created to capture this diagnosis.

Outcome 3: Timing of low dose aspirin recommendation [Assessed between initial prenatal visit to delivery (≥ 28 weeks)]

Outcome Description: Gestational age (in weeks) at the time that aspirin was first recommended (as indicated in the patient chart) between the day of the initial prenatal visit and delivery (≥ 28 weeks).

Outcome 4: Timing of low dose aspirin initiation [Assessed between initial prenatal visit to delivery (≥ 28 weeks)]

Outcome Description: Gestational age (in weeks) at the time that aspirin was initiated (as indicated in the patient chart) between the day of the initial prenatal visit and delivery (≥ 28 weeks)

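### Outcome 1 is named for aspirin intake but read only from the medication record, which accepting the alert itself writes to

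*Combined protocol and SAP*

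**What the plan says.** Outcome 1, under Other pre-specified outcome measures, is titled as patient intake and described so: "Patient chart indicates that the patient took aspirin (yes/no) during the pregnancy and up until delivery". The time frame reads "Time Frame: Assessed at time of delivery (≥ 28 weeks" weeks or later being the population as well. One capture rule follows: "The outcome is captured by aspirin being on the qualifying patient's medication record". No patient report, dispensing data, note search or check of the record at delivery is described for this outcome.

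The Methods section says that, when the alert fires, the provider may "accept the BPA recommendations (to prescribe LDA and to add this medication to the medication list") or reject it with a reason. The listed reasons include "patient declined, patient allergic to aspirin, patient taking aspirin, patient does not meet ACOG criteria for LDA". In the control arm the women's "health care provider will not receive a BPA; the pregnancy management will be based on" the provider's usual practice. The study question under Primary Outcome describes the alert as one that "recommends and facilitates LDA prescribing".

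For the primary outcome the same kind of entry serves as evidence of a recommendation: "The outcome is captured either by aspirin being added to the patient's medication record", or by a search of the notes. Analysis Notes assigns every outcome an OLS regression on arm. No allowance for misclassification is stated.

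**The concern.** The alert is the intervention, and one of the two things that accepting it does is to create the entry that Outcome 1 counts. Control patients can acquire an entry only through ordinary practice. A higher rate in the experimental arm could therefore arise partly because the alert produced more entries, whether or not all of those patients took the drug.

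As labelled, a positive result would be reported as more patients taking aspirin. What the source supports is that more patients had aspirin on the record.

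A secondary matter is the window. The time frame points to delivery, the description covers the pregnancy up to delivery, and the capture sentence carries no date.

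**Working it through.** **Texts side by side.**
- Construct (Outcome 1 description): the patient took aspirin.
- Measurement (Outcome 1 capture rule): aspirin is on the medication record.
- Intervention (Methods): acceptance prescribes aspirin and adds it to the medication list, in the experimental arm only.
- Link: the documents say *list* in one place and *record* in the other. That these are one field is a close inference, not a stated fact.

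**When a recorded difference departs from a difference in use.** Let L_E and L_C be the record rates in the experimental and control arms, s the share of entries that reflect use (taken as equal in both arms), and u_E and u_C the proportions of patients who use aspirin without an entry.

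- Recorded difference = L_E − L_C
- True difference in use = s(L_E − L_C) + (u_E − u_C)
- Recorded minus true = (1 − s)(L_E − L_C) − (u_E − u_C)

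The difference in use is overstated only when this last quantity is positive: the unused extra entries must not be offset by off-record use. The documents give no value for s, u_E or u_C.

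**Illustration.** The plan states no figure for Outcome 1, so there is nothing to reproduce. Inputs:
- 320 per arm: 640 (Power Analysis) split 1:1 (Methods).
- L_C = 60%: assumed, borrowed from the baseline *recommendation* rate in Objectives.
- L_E = 70%, that is, 10 extra recorded points: assumed.
- u_E = u_C = 0: assumed.
- Two-sided 5% level, z = 1.96: assumed.

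SE = √[(0.60×0.40 + 0.70×0.30)/320] = √(0.45/320) = 0.0375.

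The probability that the 95% interval misses the true difference is Φ(−1.96 + d) + Φ(−1.96 − d), with d = 0.10(1 − s)/0.0375.

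| s | Use, control | Use, experimental | True difference | Recorded ÷ true | d | Interval misses truth |
|---|---|---|---|---|---|---|
| 0.9 | 54% | 63% | 9 points | 1.11 | 0.267 | 0.058 |
| 0.8 | 48% | 56% | 8 points | 1.25 | 0.533 | 0.083 |
| 0.6 | 36% | 42% | 6 points | 1.67 | 1.067 | 0.187 |
| 0.5 | 30% | 35% | 5 points | 2.00 | 1.333 | 0.266 |

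The nominal miss probability is 0.05. With control record rates of 50% or 40% and the same 10 extra points, the last column becomes 0.058, 0.080, 0.176 and 0.248.

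**What survives in this setting.** With equal s and no off-record use, the true difference is s times the recorded one. It is zero exactly when the recorded difference is zero, so the test of no difference is valid. The ratio is unchanged: 70/60 = 56/48 = 1.17. Only the risk difference is scaled.

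**Off-record use.** At s = 0.8 the excess is 0.2 × 10 = 2 points. If off-record use were 2 points higher in the experimental arm, the excess would vanish; if more than 2 points higher, the recorded difference would understate the true one. This is conceivable, because a rejection on the ground that the patient already takes aspirin is not said to create an entry. Higher off-record use among controls would push the other way.

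**The case against.** The strongest reply is that this is a disclosed chart proxy. The description opens by referring to what the chart indicates, and the capture rule is stated openly. The entry also comes with a prescription, which is the intended route to intake, so some added entries are real use. Patients who decline or are allergic can be kept off the list through the rejection reasons. Control providers can prescribe and list aspirin too, and nothing says that their entries reflect use any differently. All of this stands, and it limits the point. It does not remove it: disclosing the rule does not turn an order entry into intake, the rejection reasons screen out only what is known at the visit, and no step that confirms use or removes unused entries is described.

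The illustration is also mild. The expected interval is about 10 ± 7.4 points, which contains 9, 8, 6 and 5, and at 90% real use the miss probability barely moves.

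On the window, the time frame and the phrase about aspirin *being on* the record, against *being added* for the primary outcome, favour a reading at delivery. Only on the any-time reading would Outcome 1 nearly duplicate the medication-record part of the primary outcome in the same patients. The window is therefore a point of wording.

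A reader might infer that Outcome 1 is bound to exaggerate the effect on intake, or that it could readily turn significant with no added use at all. The documents support neither. The first depends on off-record use, about which they are silent. The second needs entries in the experimental arm to reflect use less often than those in the control arm, for which they give no evidence.

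**Conclusion.** The point holds in a limited form. Outcome 1 is titled as intake but measured in a field that the intervention very probably writes to in one arm, so a difference between arms can partly reflect entries generated by the alert. The size and net direction of any bias cannot be determined from the documents. The scaling factors of 1.11 to 2.00 rest on an equal share of used entries in both arms, no off-record use and assumed record rates; they show how the problem works and are not estimates for this trial.

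The primary outcome is not affected, since there the entry is taken as evidence of a recommendation, which is what it records. Outcome 1 is neither primary nor secondary, so the stakes are low. What changes is the claim that the trial may make from it.

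**What to change.** Before any analysis by arm:

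1. Relabel Outcome 1 as *aspirin on the medication record at delivery*, or state the other window if that is intended.
2. State that it is a proxy which the intervention can change directly, and that it will not on its own be reported as a difference in patients taking aspirin.
3. As a descriptive aid, use the alert responses already collected for Outcome 6 to tabulate, in the experimental arm, how many entries came from an accepted alert and how many rejections on the ground that the patient already takes aspirin had no entry. This shows where entries came from. It does not show intake.

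The cost is a few sentences in the SAP, a small extra table from data in hand, and a less ambitious label. No new data collection or change in sample size is needed.

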Outcome 5: Preterm delivery [Time Frame: Assessed at delivery]

Outcome Description: Patient chart indicates that the patient experienced a preterm delivery (yes/no) during the pregnancy. The outcome will be assessed at two time points, ≥ 28 weeks (so that patients were allowed the full window for low dose aspirin initiation) and ≥ 20 weeks (excluding miscarriages and earlier terminations of pregnancy). The outcome is captured by a diagnosis of preterm delivery on the qualifying patient's chart noted either by chart review or an algorithm that was created to capture this diagnosis.

Outcome 6: Provider response to best practice alert [Time Frame: Assessed between initiation prenatal visit to delivery (≥ 28 weeks)]

Outcome Description: Data from the best practice alert will inform the study team of which responses are selected by the provider when responding to the best practice alert. Selection of prespecified responses by the provider will be reviewed on a weekly basis during the study period to assess whether the best practice alert triggering criteria needs to be adjusted.

Outcome 7: Number of times the best practice alert fired for a patient [Time Frame: Assessed between initial prenatal visit to delivery (≥ 28 weeks)]

Outcome Description: The BPA will stop firing once the BPA has been successfully addressed. Data from the BPA will inform the study team the number of times the BPA fired for a qualifying patient.

Analysis Notes

Recent work suggests that OLS regressions are appropriate in randomized experiments with binary outcome variables such as ours (Gomila, 2021).

Each analysis for the specified outcomes will be run using an OLS regression to examine whether the outcome differs as a function of experimental arm. For all analyses, if the distribution for a continuous outcome is positively skewed, a negative binomial or other appropriate model may be used instead.

As the treatment variation is at the individual level, we will report heteroskedasticity-robust standard errors. We will also explore the impact of clustering these standard errors at the clinic and clinic-date levels to allow for dependence across observations within these clusters. We will also investigate heterogeneity across clinics that vary along characteristics of interest, including prior-year recommendation rates.

References:

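### Outcomes 3 and 4 are gestational ages regressed on arm alone; adjusting for gestational age at the initial prenatal visit would remove variation that the alert cannot affect, at almost no cost

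*Combined protocol and SAP*

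**What the plan says.** Among the other pre-specified outcome measures, Outcome 3 is "Gestational age (in weeks) at the time that aspirin was first recommended (as indicated in the patient chart" and Outcome 4 is "Gestational age (in weeks) at the time that aspirin was initiated". Both are absolute gestational ages, not times since entry, and both are observed from the initial prenatal visit onwards.

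Under Methods, patients are eligible if they "initiate prenatal care within Geisinger prior to 28 weeks gestation". The plan gives no lower limit, distribution or standard deviation for entry age.

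The Analysis Notes use one model throughout: an "OLS regression to examine whether the outcome differs as a function of experimental arm". Three further provisions bear on this:

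- a negative binomial or other model may replace OLS if a continuous outcome is positively skewed;
- standard errors are heteroskedasticity-robust;
- clustering by clinic and clinic-date will be explored.

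No baseline covariate is named for any outcome.

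**The concern.** Gestational age at first recommendation is, in essence, gestational age at the initial visit plus the delay until the recommendation. The alert can shorten the delay but cannot change when a patient first came for care. In a regression on arm alone, all the spread in entry age is counted as noise around the arm effect. A skew-triggered change of model does not address this. Robust or clustered standard errors change how the error is estimated but do not remove the variance due to entry age.

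Two things are at stake. The first is precision: these are the plan's only measures of whether the alert brings aspirin forward within the 12 to 28 week window that the SAP itself cites. The second is imbalance: if the patients with a recorded recommendation entered care later in one arm than in the other, that difference appears in the arm contrast even when the delay is the same.

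**Working it through.** **The plan's own figures.** The plan states no standard deviation, precision target or power for Outcomes 3 and 4, so there is nothing to reproduce for them. Its only design figure, 640 patients, concerns the recommendation rate. It comes without alpha, sidedness, numerical power or a target rate, so it cannot be uniquely reproduced. It is used here only to set rough group sizes.

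**Inputs from the documents.** 640 patients at 1:1 gives 320 per arm. The current recommendation rate is 60%. Entry is before 28 weeks. The initiation window opens at 12 weeks.

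**Assumed inputs.** The experimental-arm rate is taken as 70%. The recommended patients then number 0.60 × 320 = 192 and 0.70 × 320 = 224 (190 and 225 in the simulations). All standard deviations (SDs) and delay distributions below are also assumptions.

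**Step 1: closed form, with no 12-week floor and entry independent of delay.**

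- Unadjusted SE = √(SD_entry² + SD_delay²) × √(1/192 + 1/224), where the second factor is 0.0984.
- Adjusted SE = SD_delay × 0.0984.
- Ratio of adjusted to unadjusted SE = √(1 − R²), with R² = SD_entry² / (SD_entry² + SD_delay²).

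| SD entry (wk) | SD delay (wk) | R² | SE unadjusted | SE adjusted | Cut |
|---|---|---|---|---|---|
| 2 | 4 | 0.20 | 0.440 | 0.393 | 11% |
| 4 | 4 | 0.50 | 0.556 | 0.393 | 29% |
| 4 | 2 | 0.80 | 0.440 | 0.197 | 55% |
| 6 | 3 | 0.80 | 0.660 | 0.295 | 55% |

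Halving the SE needs R² above 0.75, that is, an entry SD above √3 ≈ 1.73 times the delay SD.

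**Step 2: simulation of the proposed model.** The model is OLS on arm, gestational age at entry and max(gestational age at entry, 12). Delay is exponential with mean 2, 4 or 6 weeks, and there are 1000 to 1500 runs per cell. The floor stands for recommendations that wait for week 12. Results carry a few percentage points of simulation error.

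| Assumed entry pattern (SD) | Floor | SE cut |
|---|---|---|
| Nearly all before 12 wk (2) | yes | 0% at all three delays |
| Nearly all before 12 wk (2) | no | 30%, 9%, 5% at mean delay 2, 4, 6 |
| 95% at 7–12 wk (2.9) | yes | 30%, 10%, 6% |
| Right-skewed (3.3) | either | 3–50% |
| 90% at 7–12 wk (3.7) | yes | 41%, 17%, 10% |
| 80% at 7–12 wk (4.8) | either | 54–64%, 29–37%, 13–23% |
| Uniform 6–28 wk (6.3) | either | 23–69% |

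No cell showed a material increase in SE.

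**Step 3: entry imbalance among recommended patients (illustration, all inputs assumed except the 60%).** Let 80% of patients enter at a mean of 9.5 weeks and 20% at a mean of 20 weeks. Suppose control providers recommend aspirin to 65% and 40% of these groups, which is 0.52 + 0.08 = 0.60 overall. Suppose the alert arm recommends it to 70% of both.

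- Control mean entry age among recommended patients: (0.52 × 9.5 + 0.08 × 20) / 0.60 = 10.9 weeks.
- Alert arm: 0.80 × 9.5 + 0.20 × 20 = 11.6 weeks.

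With identical delays, the arm-only contrast would show recommendation 0.7 weeks later under the alert. Adjusting for entry age removes that component.

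**The case against.** The strongest reply is that the gain may be nil. If almost everyone enters before 12 weeks and recommendations wait for the window to open, entry age explains almost nothing. The simulation confirms a 0% cut in that setting, and nothing in the documents rules it out. This stands, and it is why no minimum gain can be claimed.

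A reader might infer that most of the confidence interval is avoidable noise, or that the intervals will certainly be much wider than they need be. The documents do not support either. A cut above 50% needs entry to vary about 1.73 times as much as delay, and the plan gives neither SD. Nor is there a guaranteed 20% saving: figures of that size as a minimum appear only if the narrower entry patterns are left out.

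It is also fair to say that the plan does not forbid covariates, and that omitting one from a randomised comparison costs precision without in itself causing bias. Both are true. But a covariate added after the results are seen is a discretionary choice, and naming it now avoids that.

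The entry-plus-delay account also has limits. The outcome clock starts at the initial prenatal visit, while patients are randomised as they attend appointments, and the documents do not say that these are the same visit. One listed reason for rejecting the alert is that the patient already takes aspirin, so some initiations may precede randomisation. This bears on which covariate to use, not on whether to adjust.

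Finally, both outcomes exist only for patients recommended or started on aspirin, a subset that the alert is meant to change. The simulations treat that subset as if it had been randomised. Adjustment removes measured entry imbalance but does not restore a fully randomised comparison. This stands in full.

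**Conclusion.** The point holds as a low-severity improvement in precision. The plan leaves out of the model for Outcomes 3 and 4 a baseline quantity that is close to a component of both, and that the trial must in effect hold in order to date the pregnancies. Across entry SDs of 2 to 6.3 weeks, mean delays of 2 to 6 weeks, and with or without a 12-week floor, adjustment cuts the SE by about 0% to about 70% and never materially raises it. Where the trial falls in that range depends on an entry distribution that the documents do not give.

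A reader might take this to mean that the arm-only analysis is invalid, or that adjustment makes the timing comparison sound. Neither follows. Omitting the covariate is a loss of efficiency, and the restriction to recommended or treated patients remains after adjustment. The primary and secondary outcomes are unaffected.

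**What to change.** Add to the Analysis Notes, for Outcomes 3 and 4 only:

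- Fit OLS on arm, centred gestational age at the initial prenatal visit (or at randomisation, if that is the same visit), and a second term max(gestational age, 12), which lets the slope change where the window opens.
- Keep the heteroskedasticity-robust standard errors.
- Report the arm-only estimate alongside.
- State that both outcomes are defined only for patients recommended or started on aspirin, so the arm comparison is conditional on a post-randomisation event and the adjustment does not fully repair this.

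The cost is a short SAP addition and two extra model terms. The visit date and pregnancy dating should already be available, since the outcomes cannot be computed without them. The documents do not say so expressly, so this should be confirmed.

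### Outcomes 2 and 5 each have a ≥28-week analysis that selects on delivery timing after randomisation, and the plan does not say whether it or the ≥20-week analysis carries the conclusion

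*Combined protocol and SAP*

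**What the plan says.** Under *Other pre-specified outcome measures* in the SAP, Outcome 5 is defined as: "Patient chart indicates that the patient experienced a preterm delivery (yes/no) during the pregnancy". Its assessment is then split: "The outcome will be assessed at two time points, ≥ 28 weeks (so that patients were allowed the full window" for aspirin initiation, "and ≥ 20 weeks (excluding miscarriages and earlier terminations of pregnancy). The outcome is captured by a diagnosis of preterm delivery". Outcome 2 is split in the same way: "and ≥ 20 weeks (excluding miscarriages and earlier terminations of pregnancy). The outcome is captured by a diagnosis of preeclampsia".

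Both outcomes are assessed at delivery, and the ≥20-week version is explained by which pregnancies it leaves out. So the two versions differ in who is analysed, not in when anyone is measured.

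The *Analysis Notes* apply one model throughout: "Each analysis for the specified outcomes will be run using an OLS regression to examine whether the outcome differs as a function of experimental arm". The plan does not rank the two versions, say how a disagreement between them would be read, or mention that the ≥28-week version conditions on something that happens after randomisation.

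**The concern.** Limiting a set to deliveries at ≥28 weeks has a rationale when the outcome is whether a provider made a recommendation. It is harder to defend when the outcome is delivery timing, or a disease that can bring delivery forward, because the outcome then helps decide who is analysed.

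The protocol's premise makes this relevant: "Low dose aspirin (LDA) has been found to reduce the incidence of preeclampsia in high-risk pregnant patients". If the alert raises aspirin use and aspirin alters early deliveries, the two arms lose different patients at the 28-week cut, and the remaining groups are no longer protected by randomisation.

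Preeclampsia and preterm delivery are the trial's only two clinical outcomes. The ≥28-week set is listed first and matches the primary outcome's population, so it could become the headline result by default. Two unranked analyses of one outcome also leave room for selective emphasis.

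**Working it through.** **The plan's own figures.** The documents give no event rate or target effect for Outcomes 2 or 5. The only sample size, 640 plus 10% (*Power Analysis*), concerns the recommendation rate. It cannot be reproduced uniquely, because alpha, sidedness, power and target rate are not stated. It is used here only for scale: "Eligible patients will be randomized in a 1:1 fashion to a control or experimental group" gives 640/2 = 320 per arm.

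**Step 1. Is the 28-week cut post-randomisation?** The *Methods* section says: "Pregnant patients who receive and initiate prenatal care within Geisinger prior to 28 weeks gestation will be included". *Project Status* has patients randomised as they attend appointments. Delivery before or after 28 weeks is therefore normally determined after allocation.

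**Step 2. Who is removed?** For Outcome 5, everyone delivering at 20–27 weeks, all of whom are preterm events. For Outcome 2, preeclampsia cases only if they also deliver before 28 weeks; early-onset disease with later delivery stays in.

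**Step 3. Effect on the comparison (Outcome 5).** Let e be the share of an arm delivering at 20–27 weeks and l the share delivering preterm at 28 weeks or later, among all who reach 20 weeks.

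- Risk in the ≥20-week set: e + l
- Risk in the ≥28-week set: l / (1 − e)

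Assumed control arm: e = 0.03, l = 0.15. This gives 18.0% at ≥20 weeks and 0.15/0.97 = 15.46% at ≥28 weeks.

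| Assumed alert effect | Alert e, l | ≥20-week risk, difference | ≥28-week risk, difference |
|---|---|---|---|
| Uniform 25% relative reduction | 0.0225, 0.1125 | 13.50%, −4.50 (RR 0.750) | 11.51%, −3.95 (RR 0.744) |
| Half of early deliveries move to term | 0.015, 0.15 | 16.50%, −1.50 | 15.23%, −0.24 |
| Half of early deliveries avoided, half of those reaching only 28–36 weeks | 0.015, 0.1575 | 17.25%, −0.75 (RR 0.958) | 15.99%, +0.53 (RR 1.034) |

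Differences are in percentage points. In row 1 the relative effect is essentially unchanged (with e = 0.02, l = 0.16 the ≥28-week RR is 0.746). The absolute difference shrinks because events are rarer in the set. In row 2, 1 − 0.24/1.50 = 84% of the difference disappears. In row 3 the sign changes.

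**Step 4. Range.** The total is kept at 18% and e varied from 1% to 5%, so that 0.01 × 320 ≈ 3 to 0.05 × 320 = 16 control patients are excluded. The row 3 pattern then gives −0.25 to −1.25 points at ≥20 weeks against +0.16 to +0.93 at ≥28 weeks. For rows 2 and 3, with a quarter or a half of early deliveries avoided, the gap between the two analyses runs from about 0.2 points (a quarter, e = 1%) to about 2.2 points (a half, e = 5%).

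**Step 5. Against sampling error.** The standard error of a risk difference at 18% is √(2 × 0.18 × 0.82 / 320) = 3.04 points, larger than every gap in Step 4.

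**Step 6. Could an alert halve early deliveries?** Control recommendation is about 60% (*Objectives*). Let p be the alert-arm recommendation rate and k aspirin's relative reduction in early deliveries. Assume that everyone recommended aspirin takes it and that risk is otherwise equal. The ratio of early deliveries, alert to control, is (1 − pk)/(1 − 0.6k). Setting it to 0.5 gives k = 0.5/(p − 0.3).

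- p = 0.70: k = 1.25, which is impossible.
- p = 1.00: k = 0.71.

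Now take an assumed k = 0.5 and p = 0.70, with 6 early and 48 later preterm deliveries among 320 controls. Early deliveries fall to 6 × 0.65/0.70 = 5.57. If the avoided ones reach term:

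- ≥20-week difference: 53.57/320 − 54/320 = −0.13 points
- ≥28-week difference: 48/314.43 − 48/314 = −0.02 points

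The gap is about 0.11 points.

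**The case against.** A reader might infer that these outcomes are analysed only at ≥28 weeks, so that the earliest events are lost. The documents do not support that. The same sentence pre-specifies the ≥20-week analysis, which restores those deliveries, and any distortion would show as a gap between the two results.

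A reader might also infer that the ≥28-week comparison is always biased against the alert. That fails too: under a uniform relative effect the risk ratio is almost unchanged and moves, if anything, slightly in the alert's favour. A change of sign needs an effect concentrated before 28 weeks, with some avoided early deliveries still preterm.

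The size objection is strong. Starting from 60%, a moderate rise in recommendation cannot halve early deliveries (Step 6), so rows 2 and 3 show direction and not an expected size. These are also neither the primary nor the secondary outcome, and the sample size was not set for them.

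The full-window reason deserves a fair reading. The primary outcome description gives the window as 12 to 28 weeks, and a patient entering at 24 weeks and delivering at 26 had only two weeks of it. But the rule does not secure a full window either. Someone starting care at 27 weeks and delivering at term is kept with about one week, while someone in care from 12 weeks and delivered at 26 is excluded with 14 of 16.

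Finally, the ≥20-week set is itself partly selected, because patients may be randomised before 20 weeks. That stands and is reflected in the fix.

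None of this answers the remaining question: if the two results differ, the plan does not say which to believe.

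**Conclusion.** The point holds as a matter of estimand and ranking. The ≥28-week analyses of Outcomes 2 and 5 condition on a post-randomisation event. For Outcome 5 that event overlaps with the outcome itself, and no lead analysis is named.

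The consequence is conditional. Understatement or a change of sign is arithmetically possible if the effect lies before 28 weeks or carries deliveries across that line. It is negligible on the ratio scale under a uniform effect. At the counts considered it stays below the standard error, and is about 0.1 point under the milder assumptions of Step 6. Every event rate, the value of k and the alert-arm recommendation rate are assumptions, since the documents supply none of them.

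This is a worthwhile low-cost correction to two supporting outcomes. It does not bear on the primary comparison.

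**What to change.** In the SAP text for Outcomes 2 and 5:

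- State that conclusions rest on the already planned ≥20-week set, with all deliveries at 20–27 weeks counted as preterm for Outcome 5.
- Keep the ≥28-week version only as a labelled descriptive analysis, noting that it is subject to selection after randomisation.
- Call the two versions analysis sets, not time points.
- Report by arm the number excluded at 20–27 weeks and the number excluded before 20 weeks, so that selection into either set is visible.

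This costs SAP wording and one small table; no new data or analysis is needed. The downside is that the clinical outcomes no longer use the same set as the primary outcome, which one explanatory sentence can cover.
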